### 3.1 Summary of Prior Clinical Experience

We conducted two studies on the safety and efficacy of TLT delivered to the forehead (prefrontal cortex) twice a week in subjects with MDD.

ELATED-1 was a proof of concept study of 3 weeks of TLT (Neurothera - class IV laser, wavelength 808 nm; irradiance 700 mW/cm^2; fluence of 84 J/cm^2; total energy 2.4 kJ per session for 6 sessions) ([name] et. al. 2015). All subjects (n=4) were treated with TLT. Baseline mean HAMD-17 scores for depression decreased from 19.8±4.4 (SD) to 13±5.35 (SD) after treatment (p=0.004).

ELATED-2 was a double-blind, randomized, controlled study of 8 weeks of TLT (Omnilux New U - LED, 830 nm; 36.2 mW/cm^2; up to 65.2 J/cm^2; vs. sham for 16 sessions). At endpoint, the mean HAMD-17 for depression decreased of 11.7±7.5 points (TLT, n=9) vs. 5.3±7.0 points (sham, n=9) (p=0.04); the differences were even more pronounced in the completers sample as HAMD-17 decreased of 15.7±4.4 (TLT, n=6) points vs. 6.1±7.9 points (sham, n=7) (p=0.01).

These findings suggest that TLT could be a novel intervention for patients with MDD. Both the Laser study (ELATED-1) and the LED study (ELATED-2) were conducted by our group at MGH. ELATED-3 (the present submission) will test for the first time pulse light therapy (p-TLT) in a comparable population of MDD subjects.

The LiteCure® PhotoBioModulation-1000 (TPBM-1000) device to be used in this study does not require FDA approval. In fact, the TPBM-1000 device used in this study is considered a non-significant risk device because:

- TPBM -1000 dose does not exceed the Maximum Permissible Exposure (MPE) for skin – Center for Devices and Radiological Health (CDRH), 21CFR1040.10 and 21CFR1040.11;
- TPBM-1000 is substantially equivalent to the OmniLux New U device (used in ELATED-2 at MGH), which the FDA has already categorized as a non-significant risk device;
- TPBM-1000 differs from the OmniLux New U only in that it provides an additional site of irradiation – treatment is delivered to EEG sites FP1 and FP2 in addition to F3 and F4 on the forehead;
- currently FDA-cleared LED devices are typically available over-the-counter and are considered safe to use without professional supervision.

### 3.2 Overview of LiteCure Laser System

LiteCure® TPBM-1000 is a new device with the flexibility to safely deliver either continuous or pulsed light: c-TLT or p-TLT, or sham. The TPBM-1000 device is configured for in-office use.

TPBM-1000 delivers NIR light output at 830 +/- 30 nm. The NIR output is invisible to the naked eye, thus, the device includes visual and/or audible indicators of light emission, and is designed to deliver light to EEG sites: Fp1, Fp2, F3 and F4, covering a total surface active treatment area, of 35.8 cm^2[(11.52 cm^2x2) + (6.38 cm^2x2)] with an average irradiance of 54.8 mW/cm^2 and an average fluence of 65.8 J/cm^2. While the average fluence (energy density) is comparable to the Omnilux New U, the treatment area is significantly less for the TPBM-1000 (Omnilux New 28.7 cm^2 x2, which results in less total energy delivered per session of 2.3 kJ (compared to up to 3.7 kJ for the Omnilux New U).

TPBM-1000 devices will be fabricated to deliver either c-TLT, p-TLT, or Sham. In simple terms, in either TLT mode the TPBM-1000 device delivers therapeutic NIR energy; in sham the device will not deliver any light energy. The apparent behavior (i.e. the performance/output of all visible and audible indicators) of the device in any of the three programmed treatment modalities will be identical, ensuring the study is blinded to the operator. In addition, because of the low average irradiances delivered in either c-TLT and p-TLT modes the patients will not experience any heating sensation ensuring the study is double-blind.

The TPBM-1000 devices consists of a source of light, mounted on a cap, attached to a console that controls the light delivery modality: c-TLT, p-TLT, or Sham.

### ***3.3 Overview of Rationale for Cognitive Tasks, and for neuroinflammatory laboratory tests.***

#### Cognitive Tasks

The prefrontal cortex (PFC) and dorsal lateral prefrontal cortex (DLPFC) are uniquely situated to play a critical role in learning, executive functions, attention and inhibition. Studies have shown that DLPFC exhibits significant plasticity during the learning process, in which neuronal activity changes to dynamically encode and re-code procedural memories once a sensory motor association has been made. The purpose of this study is to determine whether TLT can be used to change the speed at which subjects learn and perform in cognitive tasks. TLT applied to prefrontal regions of the brain implicated in visual-motor learning processes can enhance neural plasticity and improve behavioral performance.

#### Neuro-inflammatory laboratory tests

Animal and clinical research suggest that the inflammatory immune system contributes to MDD. Post-mortem gene expression profiling on tissue samples from Brodmann area 10 (BA10 – prefrontal cortex) have shown that MDD is characterized by increased inflammation and apoptosis (Shelton et al., 2011). In a case-control study, Simon and colleagues (2008) found that antidepressant-naive MDD subjects had significant elevations in the following cytokines and chemokines when compared to healthy controls: MIP-1 $\alpha$ , IL-1 $\alpha$ , IL-1 $\beta$ , IL-6, IL-8, IL-10, Eotaxin, GM-CSF, and IFN $\gamma$ .

Although IL-10 is an anti-inflammatory cytokine, the results suggested that the elevated levels of this IL-10 were likely induced in response to the overall elevation of pro-inflammatory cytokine levels (Simon et al., 2008). In a review of the research on inflammation in MDD, Raison, Capuron, and Miller (2006) proposed that pro-inflammatory cytokines might cause brain abnormalities that are characteristic of MDD. Indeed, animal research has shown that IL-1 mediates chronic depression in mice by suppressing hippocampal neurogenesis (Raison et al., 2006; Goshen et al., 2007).

One pro-inflammatory cytokine that may be of particular relevance to depression is CSF IL-6 (IL6 measured in cerebrospinal fluid). In a recent report, patients with MDD had significantly higher CSF IL-6 levels compared to healthy controls; CSF IL-6 levels were significantly higher than in the serum and there was no significant correlation between CSF and serum IL-6 levels (Sasayama et al., 2013). These findings are consistent with a prior report showing a positive correlation between CSF IL-6 levels and the severity of depression and suicide attempts, with the strongest correlation found in violent suicide attempters (Lindqvist et al., 2009). One report in a smaller sample of depressed patients has shown that CSF IL-6 was lower or comparable to healthy controls (Levine et al., 1999).

Near-infrared light and red light (600-1600 nm) decreased synovial IL-6 gene expression (decreased mRNA levels) in a rat model of rheumatoid arthritis (Araki et al., 2011). In another study, NIR (810 nm) used as a treatment for pain in patients with rheumatoid arthritis decreased production of the following pro-inflammatory cytokines: TNF- $\alpha$ , IL-1 $\beta$ , and IL-8 (Yamaura et al., 2009). Khuman and colleagues (2012) showed that transcranial NIR improved cognitive function and reduced neuroinflammation as measured by Iba1+ activated microglia in brain sections from mice that had suffered a traumatic brain injury. Finally, NIR (970 nm) has been found to be an effective treatment for inflammatory-type acne (Barolet and Boucher, 2010). In summary, it is reasonable to predict that transcranial NIR treatment would likewise have an anti-inflammatory effect in patients suffering from MDD.

## 2. Investigational Plan

### 4.1 Rationale

The specific aims of this study are:

1. To assess the antidepressant effect of the continuous and pulse Transcranial Light Therapy in depressed subjects.
2. To assess the safety and tolerability of the continuous and pulse Transcranial Light Therapy in depressed subjects
3. To pilot test the impact on cognitive functioning and neuro-inflammation of the continuous and pulse Transcranial Light Therapy in depressed subjects

#### Rationale for the use of this device in individuals with MDD:

Different devices have been used in the study of near-infrared radiation (NIR) treatment effects in humans. We decided to use a new device, created by Litecure

specifically for this study in order to allow, in the same setting, testing of both continuous and pulse NIR in a blind fashion and with adequate control (sham).

## 4.2 Study Design

This study is a double-blind, placebo-controlled, sequenced parallel study on the use of Transcranial continuous light therapy (PART 1 – TLT-c) and pulse light therapy (PART-2 TLT-p) as treatment for depressive symptoms in patients with Major Depressive Disorder (MDD).

This study will include up to 50 subjects randomized at a 1:2 ratio into 2 groups: Transcranial Light Treatment (TLT) and sham.

All subjects will receive 2 TLT/sham treatments per week for 12 weeks. Subjects randomized to the sham group will receive sham treatments for the first 6 weeks; during weeks 7-12 subjects in the sham group will be re-randomized to either TLT or to sham. All subjects and investigators (except the study statistician) will be blind to treatment sequence assignment.

Treatment group assignment will be decided by randomization and managed by the study statistician. Each study site (MGH and NYUSOM) will have one Litecure device, which will recognize the randomization codes generated by the study statistician. For each randomized subject a sealed envelope with treatment assignment will be available at the respective study site. Both subjects and study staff will be blind to the treatment group assignment. The Sham treatment consists in applying all the procedures for the delivery of the TLT, while actually delivering no light. The blinding of the sham will be effective because the radiation is not visible and because the active therapy (continuous or pulsed) will not produce any patient discernable difference from sham, e.g., skin warming. The sham treatment will mimic the TLT procedure. The treatment will be bilateral and applied to the frontal areas with two application sites on the left side and two on the right side [left and right forehead centered on EEG sites on F3, F4, Fp1, Fp2]. Energy is administered with a radiation wavelength of 830 nm. The duration of irradiation is 20 minutes at each application site (the 4 sites are irradiated at the same time which is equivalent to 20 minutes of total time), while the entire session is estimated as lasting 25 minutes or less (Schiffer et al., 2009) (Lampl et al., 2007, Zivin et al., 2009). The additional 5 minutes are needed to prepare the subject, to place the necessary protections (e.g. goggles), to inspect the subject's skin, to set the TLT devices and to give time to rest to the subject after the irradiation. TLT treatment will only be administered by licensed physicians (i.e. MDs) who are on study staff. All staff who deliver treatment must pass training that is approved by the MGH and/or NYUSOM Laser Safety Committee. The duration of irradiation will be decreased if clinically indicated, based on tolerability to 15 min as needed. The treatment will follow these specifications: wavelength 830 nm; average irradiance 54.8 mW/cm^2; average fluence of 65.8 J/cm^2 (consistently with parameters used in the ELATED-2 study at MGH with the device Omnilux New U).

Subjects diagnosed with major depressive disorder who meet all inclusion criteria, have none of the exclusion criteria, and are willing to undergo the Informed Consent process will be eligible to participate in this clinical study.

### ***4.3 Study Population***

#### **4.3.1 Population Description**

The subject population for this study will consist of 50 subjects between the ages of 18 and 70, of any ethnic background and diagnosed with major depressive disorder. The subject will meet all the inclusion criteria, have none of the exclusion criteria, and provide their written Informed Consent to participate in this clinical study. Any subject who signs informed consent will be considered enrolled into the study, although they may not participate if they do not qualify for the study. In the event that a subject's ability to comprehend and communicate is compromised (per the assessment of the Investigator), local regulations pertaining to Informed Consent signatures should be followed.

Subjects will be recruited, via screenings, advertisements and postings. Study participants will also be recruited via internet-based advertisements, e.g., Craigslist, Clinical Trials @ Partners, the study sites websites, RSVP for Health (which will also generate listserv emails to Partners employees, regarding research studies in need of volunteers), etc.

Participants who contact the respective study site staff in response to any of the aforementioned advertisements will complete phone screening questions to determine tentative eligibility for the study.

#### **4.3.2 Use in Female Subjects of Childbearing Potential**

Female subjects of childbearing potential must consent (without any element of coercion) to use a double-barrier method for birth control (e.g. condoms with spermicide) if sexually active. A pregnancy test will be performed at the Screening Visit.

#### **4.3.3 Criteria for Enrollment – listed on pages 5-6**

### ***4.4 Subject Numbering***

Subjects enrolled in the ELATED-3 study will be identified by subject numbers 101 through 99 (to account for screen failures and drop-out before randomization).

### ***4.5 Sample Size***

The ELATED-3 Study is expected to include 50 subjects with analyzable data (at least 1 session post randomization).

#### **4.6 Subject Confidentiality**

Any information and data provided to Litecure Inc. or its designees in reference to any subject's participation in this investigation will be considered confidential. The Investigator will need to ensure that all subjects' anonymity will be maintained on all documentation submitted to Litecure Inc by completely redacting (eliminating or "blacking out") each subject's name and/or other identifying information. The identifying information will be replaced with the subject's study number and initials. The investigational site is not to provide to Litecure Inc information such as subject's telephone numbers, home address, personal identification numbers such as passport numbers, etc. Care must be taken by site research personnel when communicating with representatives from Litecure Inc in the form of telephone or electronic correspondence in not providing information that may disclose a subject's identity.

Documents associated with the study that are not intended to be submitted to Litecure Inc (e.g., signed Informed Consent Forms) must be kept in strict confidence by the Investigator. Only study site personnel, authorized Litecure Inc personnel, and regulatory authority inspectors will have access to these confidential files.

#### **4.7 Study Visits**

Study visits occur at MGH Depression Clinical and Research Program (DCRP) in Boston and at the NYUSOM Nathan S. Kline Institute (NKI) site in Orangeburg, NY.

The study involves screening, treatment, and a series of follow-up visits.

##### Screening Visit (Week -1)

The Principal Investigator (PI) at the site or a Sub-investigator will assess patients against the inclusion and exclusion criteria. If a patient appears to qualify and agrees to participate in the study, then the patient will undergo the informed consent process prior to initiation of any study-specific activities. Screening Case Report Forms (CRFs) will be completed and subjects who qualify to participate in the study will proceed to the first Treatment Visit 1. If the subject does not meet entry criteria, the Investigator will document the subject's ineligibility for study participation and complete the appropriate CRFs.

##### Treatment Visits – Visits 1-24 (Weeks 1-12)

There are 2 treatment visits per week for 12 weeks. This visit-schedule applies both to the PART-1 (TLT-c) and PART-2 (TLT-p) phase of the study. Treatment Visit 1 will consist of all subjects being randomized to the TLT and Sham groups and undergoing baseline assessments including HAM-D-17, QIDS-C, ASQ and cognitive tasks prior to treatment.

Treatment Visits 1-12 will include various assessments as detailed in Section 4.8 and in Attachment 1.

##### Follow-Up Visit – Visit 25

All subjects will undergo subject assessments including HAM-D-17, QIDS-C, ASQ, and cognitive tasks at follow-up Visit 25 (Week 13).

#### **4.8 Detailed Study Visits**

##### **4.8.1 Screening Visit (Week -1)**

###### Purpose

The purpose of the Screening Visit will be to determine the eligibility of patients for participation in the ELATED-3 Study.

###### Procedures

At this visit subjects will receive a psychiatric evaluation, will be consented for the study, and will be screened for presence of MDD using the MINI. The HAM-D-17, QIDS-C, SDQ and CGI will be used to assess severity of depressive symptoms, the ASQ will be used to assess anxiety symptoms, and the C-SSRS will be used to assess suicidality. The ATRQ will be used to assess resistance to treatment. The MoCA will help determining cognitive impairment that would contraindicate study participation.

Routine laboratory tests (including urine collection for Urine Analyses, Urine Tox Screen, and Urine Pregnancy Test) and complete physical exam including vitals and weight will be performed at screen; the tests will be processed by a laboratory at MGH and at NYUSOM.

About 15cc ± 5cc (15 mL) of blood is drawn for laboratory safety tests. To confirm a patient is healthy enough to participate a complete blood test with differentials, thyroid stimulating hormone test, a comprehensive 14-metabolic panel test, and a c-reactive high sensitivity protein test are conducted on screening day. An additional 2-6 cc of blood will be drawn for the cytokine assays during the screen visit.

Once all tests and procedures become available for review, the Investigator will then proceed to closely re-evaluate the subject for all the inclusion and exclusion criteria.

Subjects are allowed into the study if they did not fail more than two antidepressants in the current episode. Subjects could decide to continue their antidepressant during the study or to taper it off prior to the baseline visit.

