**Entry Criteria: Inclusion Criteria**

1. Subjects age at screening will be between 18 and 70 years old (inclusive).
2. Diagnosis of major depressive disorder (MINI)
3. HAM-D17 $\geq$ 14

4. CGI-S  $\geq 4$  or higher, i.e., “moderately depressed”
5. Women of child-bearing potential must use a double-barrier method for birth control (e.g. condoms plus spermicide) if sexually active.
6. Subject Informed Consent obtained in writing in compliance with local regulations prior to enrollment into this study.
7. The subject is willing to participate in this study for at least 12 weeks.
8. Subjects will need to be on stable dose(s) of antidepressants (if taking any) for at least six weeks prior to enrollment.

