#### ***4.8.2.1 Treatment Visit 1***

During Treatment Visit 1, subjects will be randomized to either TLT or Sham. The following will be performed prior to treatment and serve as baseline values:

- HAM-D-17
- QIDS-C
- CGI
- C-SSRS
- ADVERSE EVENTS FORM
- CADSS
- Concomitant medications form
- ASQ (self-rated)
- SAFTEE-SI (self-rated)
- SDQ (self-rated)
- NEURO-QOL (self-rated)
- SFI (self-rated)
- PEG (self-rated)
- Cognitive tests

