#### **4.8.2.2 Screening Visit, Visit 13, and Visit 25**

During these visits, approximately 2-6 cc of blood will be drawn to conduct cytokine assays.

Patients shall be instructed to contact the investigator or a member of his staff at any time between visits concerning adverse events or worsening of symptoms.

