#### **4.8.3 Post-Treatment Visit – Visit 25, (Week 13)**

After treatment completion, subjects will continue with one more clinical study visit to measure the long-term antidepressant effect of TLT. Post TLT administration, subjects will be permitted to start or change treatment with antidepressant medications, as clinically necessary (and at any time in the study if severe worsening of depressive symptoms – see 4.8.4 Termination). Cognitive testing will be performed.

At Visit 25, the following will be performed:

- Vital Signs and weight
- HAM-D-17

- QIDS-C
- CGI
- C-SSRS
- CADSS
- ADVERSE EVENTS FORM
- Concomitant medications form
- ASQ (self-rated)
- SAFTEE-SI (self-rated)
- SDQ (self-rated)
- NEURO-QOL (self-rated)
- SFI (self-rated)
- PEG (self-rated)

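### The only pre-treatment cytokine sample is drawn at screening, before any permitted antidepressant taper need be finished, and no drug-free interval is set (minor)

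*Protocol*

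**What the plan says.** **Taper.** Protocol 4.8.1 (Procedures) states: "Subjects could decide to continue their antidepressant during the study or to taper it off prior to the baseline visit". Neither document gives a taper length, a drug-free interval, or a maximum gap between screening and Visit 1.

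**Stability rule.** Inclusion criterion 8 reads: "Subjects will need to be on stable dose(s) of antidepressants (if taking any) for at least six weeks prior to enrollment". Protocol 4.3.1 defines the anchor: "Any subject who signs informed consent will be considered enrolled into the study". Criterion 6 and the note in 6.4, however, require consent steps to be complete before enrollment, which places enrollment after consent.

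**Cytokines.** At screening, "An additional 2-6 cc of blood will be drawn for the cytokine assays during the screen visit". Section 4.8.2.2, whose heading names the Screening Visit, Visit 13 and Visit 25, adds: "During these visits, approximately 2-6 cc of blood will be drawn to conduct cytokine assays". Attachment 1 shows no additional draw at Visit 1. The endpoint in the Study Summary is the week 6 and week 12 level relative to baseline.

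**Other baselines.** For Visit 1, 4.8.2.1 says "The following will be performed prior to treatment and serve as baseline values" and lists HAM-D-17, QIDS-C, the other scales and the cognitive tests. Cytokines are not on that list.

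**The concern.** Two gaps combine. A subject may arrive at Visit 1 newly off an antidepressant, and the cytokine baseline may have been taken while that subject was still on it. The clinical and cognitive baselines would then describe the off-drug state and the cytokine baseline the on-drug state. Any effect of stopping the drug would be counted in that subject's cytokine change.

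What is at stake is mainly the interpretation and precision of a small pilot readout, with about 8 TLT and 16 sham subjects per part at the first randomization. Two lesser matters follow. Discontinuation effects can add variance to the phase 1 depression scores. And a subject who has just stopped a drug has a 2/3 chance of at least six weeks of sham.

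**Working it through.** **1. Does criterion 8 close the gap?**
- If enrollment is the signing of consent (4.3.1), the six weeks end at screening and a later taper falls outside the window.
- If enrollment comes later (criterion 6, section 6.4), a subject who is off drug by then is not taking an antidepressant, so the conditional wording exempts that subject.
- Under either reading, 4.8.1 expressly permits the taper. The gap does not depend on which definition is meant.

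**2. Which sample is the cytokine baseline?** Draws occur at screening, Visit 13 and Visit 25, so baseline can only be the screening sample. That the draw precedes the taper is an inference. Section 4.7 says "the patient will undergo the informed consent process prior to initiation of any study-specific activities", so a taper made in order to join the study would normally follow consent, and probably the draw.

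**3. The plan's own power figure.** Section 5.3 claims more than 80% with 21 sham and 12 active observations. From ELATED-2 (section 3.1), all subjects: difference 11.7 − 5.3 = 6.4; variance V = (7.5² + 7.0²)/2 = 52.6; SD 7.25. Treating the 33 as independent, Φ(6.4/[7.25·√(1/21 + 1/12)] − 1.96) = 68.4% two-sided. With the completer figures (difference 9.6, pooled SD 6.55) the same formula gives 98.2%. The claim is therefore consistent with the completer effect. It is not in dispute here.

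**4. Effect on the primary comparison.** Section 5.6 weights the two phases equally, so I use

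SE = 0.5·√[V₁(1/8 + 1/16) + V₂(1/4 + 1/5)], power = Φ(6.4/SE − 1.96).

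HAM-D figures are used because the documents give no SD for QIDS-C. With V₁ = V₂ = 52.6, SE = 2.896 and power = 59.9%.

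Assume a proportion p tapers and their phase 1 change differs by d HAM-D points. This adds p(1 − p)d² to V₁. A 1-SD chance imbalance moves the weighted estimate by 0.5·d·√[p(1 − p)(1/8 + 1/16)].

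| p, d (assumed) | Added variance | SE | Power | 1-SD imbalance, points |
|---|---|---|---|---|
| 0.10, 2 | 0.36 | 2.899 | 59.8% | 0.13 |
| 0.25, 4 | 3.0 | 2.920 | 59.2% | 0.38 |
| 0.50, 6 | 9.0 | 2.968 | 57.8% | 0.65 |

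**5. Effect on cytokines.** Neither document specifies a cytokine analysis, so I take a simple TLT-sham contrast of changes. Assume stopping shifts the change by d SD. The within-arm shift is p·d. The SE factor is √[1 + p(1 − p)d²] if tapered subjects are kept and 1/√(1 − p) if they are excluded.

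| p, d (assumed) | Within-arm shift | SE if kept | SE if excluded | Left of 24 |
|---|---|---|---|---|
| 0.10, 0.2 SD | 0.02 SD | +0.2% | +5% | about 22 |
| 0.25, 0.5 SD | 0.13 SD | +2% | +15% | 18 |
| 0.50, 0.8 SD | 0.40 SD | +8% | +41% | 12 |

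The within-arm shift has the same expectation in both arms, so the expected shift in the contrast is 0.

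**6. Participants.** Of 50 randomized, 50 × 0.25 = 12.5 would taper (5 to 25 for p from 0.10 to 0.50). Two thirds of these, 8.3 (3.3 to 16.7), would be assigned at least six weeks of sham, before dropout and rescue.

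**The case against.** The strongest case against the point is that nothing of consequence follows from it. The taper decision is made before randomization, the loss of power is under one percentage point in the central case, and the cytokine aim is described as a pilot. The concomitant medications form is completed at screening and at Visit 1, so tapered subjects can be identified and adjusted for. No passage says that stopping an antidepressant changes plasma cytokines; if the true shift is zero, the cytokine figures above vanish. The one-week gap is only a nominal label (Week -1), Attachment 1 appears to number screening as week 0, and a taper that must be finished by Visit 1 may need longer. A six-week rule would also make anyone wishing to stop do so without the study's roughly weekly C-SSRS, CGI and QIDS-C ratings.

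Most of this stands, and it limits the point to a minor one. It does not remove the mismatch in timing. The form shows who tapered but cannot recover an off-drug cytokine baseline that was never drawn, and a longer gap would put the screening sample further from the start of treatment.

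A reader might infer that the taper option biases TLT against sham. The documents do not support that: the choice precedes randomization at Visit 1, and sham non-responders are randomized again at week 6. A reader might also infer that participants are left unprotected. The provisions in 4.8.4, 4.17.2 and 4.19.1 cover worsening, suicidality and withdrawal, and subjects who were already unmedicated face the same allocation.

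**Conclusion.** The point holds as a minor one. The protocol allows an antidepressant taper before Visit 1 with no drug-free interval, criterion 8 does not clearly cover a recent stop, and the only pre-treatment cytokine sample can fall on the other side of the taper from the Visit 1 baselines. The consequence is noise and chance imbalance in a secondary pilot aim, plus a within-arm cytokine change that is harder to interpret. There is no bias between arms in expectation.

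The size cannot be computed from the documents. The taper rate, the HAM-D shift and the cytokine shift are all assumptions, as is the order of draw and taper. On those assumptions the primary comparison loses about 1 point of power (59.9% to 59.2%, at worst 57.8%). The cytokine SE rises by 2% (0.2% to 8%) if tapered subjects are kept. The 15% figure arises only if they are excluded, which there is no need to do.

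**What to change.** **Main change.** Move the baseline cytokine draw from screening to Visit 1, before the first session, and amend 4.8.1, 4.8.2.2 and Attachment 1 to match. This places the cytokine baseline with the other pre-treatment baselines and after any taper. The cost is one needle stick separate from the screening safety labs; no visit or assay is added. It also spares the draw in subjects who fail screening, which 5.3 puts at half of the 100 expected to consent, so about 50.

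**Optional, a trade-off with recruitment.** Anchor criterion 8 to Visit 1 and require a stated period on the same antidepressant and dose, or on none, in place of the open-ended taper option. This removes the recent stop itself, and with a period as long as six weeks it would make the main change largely redundant. The cost is that subjects who want to stop a drug are delayed, not enrolled, or stop outside study monitoring; the documents do not say how many. The later medication provision in 4.8.3 ("Post TLT administration, subjects will be permitted to start or change treatment with antidepressant medications, as clinically necessary") and the rescue rules in 4.8.4 can stay as they are.
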